5.13.3.2 Duration of Response Assessed by RECIST 1.1 for Cohorts A and B

Duration of response will be analysed using the ITT set and only subjects who have a documented response of CR or PR will be included.

Duration of response is calculated as the time in months from the date of first documented response of CR or PR per RECIST 1.1 until the date of documented PD per RECIST 1.1 or until the date of death due to any cause (date of death or PD – date of documented response + 1). All scans are considered, whether scheduled or unscheduled, in the determination of response and confirmed responses are not required.

Subjects who neither progress nor die will be right censored on the date of their last tumour assessment. For Cohort B subjects who change treatment to IMM-101 and ipilimumab, only responses evaluated until the point of this change in therapy are included.

Summaries of duration of response

Descriptive statistics will be presented for duration of response. The number and percentage of subjects that are censored will be summarised, along with KM estimates for the 25th, 50th and 75th percentiles for the duration of response and corresponding

95% CIs. The proportion of subjects who have not progressed or died following a complete or partial response at three monthly intervals will also be presented.

5.13.3.3 Time to Response Assessed by RECIST 1.1 for Cohorts A and B

Time to response will be analysed using the ITT set and only subjects who have a documented response of CR or PR will be included.

Time to response is calculated as the time in months from Visit 1 to the first documented response of CR or PR per RECIST 1.1 (date of documented response – date of Visit 1 + 1). All scans are considered, whether scheduled or unscheduled, in the determination of response and confirmed responses are not required.

For Cohort B subjects who change treatment to IMM-101 and ipilimumab, only responses evaluated until the point of this change in therapy are included.

Summaries of time to response

Descriptive statistics will be presented for time to response. KM estimates for the 25th, 50th and 75th percentiles for the time to response and corresponding 95% CIs will be presented. The proportion of subjects who have not achieved complete or partial response at 3 monthly intervals will also be presented.

5.13.3.4 Disease Control Assessed by RECIST 1.1 for Cohort B from Week 14 Onwards

Disease control will be analysed using the ITT set for Cohort B only.

Disease control is defined as a subject with a response of CR, PR or SD as per RECIST 1.1. Confirmed responses are not required.

SD determination requires a minimum scan time of 9 weeks from the first administration of IMM-101. Therefore, the first scan to be considered for this determination is Week 14. If unscheduled scans take place earlier than Week 14 but later than Week 9, they will be used for determination of SD for disease control at Week 14. For further information on the scan windows see Section 5.2.4 of this SAP.

Disease control is assessed at each scheduled scan assessment from Week 14 until the end of the study. For subjects who change treatment to IMM-101 and ipilimumab, only responses evaluated until the point of this change in therapy are included.

Disease control rate is calculated as the number of subjects with disease control divided by the number of subjects in the analysis set.

Summaries of Disease Control

The number of subjects with controlled disease and the number without controlled disease will be summarised together with the disease control rate for each scheduled scan assessment. The binomial 95% CIs will also be presented.

Disease control will be listed for each subject in Cohort B for each Visit.

5.13.3.5 BOR Assessed by RECIST 1.1 for Cohort B Including Responses Obtained Following a Change in Therapy

The analysis as detailed in Section 5.13.1 for the primary endpoint will be repeated on Cohort B where ORR is calculated from the BOR of including assessments performed including scans performed following the change to treatment with IMM-101 and ipilimumab. Analysis will be performed on the ITT.

All scans over the entire study, whether scheduled or unscheduled, will be evaluated for overall response. Unconfirmed responses will be used in the assessment of BOR where BOR is the best overall response during the defined period and does not need to be confirmed at a subsequent timepoint. Subjects without a BOR assessment, such as those with no post-baseline responses or only NE responses, will be assumed to have a response of PD using a worst-case approach.

Summaries of BOR in Cohort B (including assessments post ipilimumab)

The BOR will be summarised and the ORR and accompanying binomial 95% CIs will also be presented.

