#### 2. Treatment Phase

All patients who are confirmed as eligible to participate in the study, and, for female participants who are not surgically sterilised or post-menopausal, have a negative pregnancy test confirmed within 72 hours of first dosing with IMM-101, will enter the Treatment Phase of the study. All patients in both cohorts of the study will receive one 1.0 mg (0.1 mL) dose of IMM-101 every 2 weeks for the first 3 doses followed by a rest period of 4 weeks, then every 2 weeks for the next 3 doses, and thereafter every 4 weeks.

Nivolumab is given every 2 or 4 weeks (dependent on Investigator choice of dosing regimen) to patients in both cohorts of the study.

In instances when nivolumab and IMM-101 are given on the same day, IMM-101 will be administered first (see Section 7.6.1).

If used on study for patients in cohort B, ipilimumab is administered every 3 weeks to a maximum of 4 doses. In instances when ipilimumab and IMM-101 are given on the same day, IMM-101 will be administered first (see Section 7.6.2).

At the discretion of the Investigator the dose of IMM-101 may be adjusted and dosing of IMM-101, nivolumab or ipilimumab delayed according to local skin reactions to IMM-101 and toxicities to all study drugs as detailed in section 7.2.1.

The Treatment Phase will continue for up to the Week 78 visit unless such therapy is contraindicated, the patient does not wish to continue, or the study is terminated by the Sponsor.

Patients will be assessed for response via scheduled scans with the first post-baseline scan at week 12 for patients in cohort A and at week 6 for those in cohort B. Subsequent scans are every 8 weeks with unscheduled scans allowed if clinically indicated, for example to confirm progression. At the discretion of the Investigator, the frequency of

Page 32 of 98

scans may be increased to every 12 weeks for patients who continue on study beyond week 52.

Patients may choose to withdraw from the study at any time and for any reason. Full details of reasons for discontinuation are in section 6.3.

Patients who discontinue study treatment or complete the study should, where possible, attend an end of study visit within 28±7 days after the final dose of IMM-101 when all previously unresolved adverse events will also be followed up. If an end of study visit is not possible any unresolved adverse events and update on concomitant medications should be followed up by other means of contact (e.g. telephone; Section 9.5).

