#### 10.6 DISEASE CONTROL

Disease Control will be assessed for patients in cohort B of the study only and is defined as those patients with a response (CR or PR) or SD based on RECIST 1.1. The minimum scan time from Day 0 (date of first IMM-101 dose) for determination of Stable Disease (SD) is 9 weeks. Stable disease for patients in Cohort B can therefore be first assessed at the second scan on study (Week 14) since the first scheduled scan is at 6 weeks. If unscheduled scans take place earlier than Week 14 but later than Week 9, these may be used for determination of SD. The disease control rate is evaluated for treatment with IMM-101 + nivolumab only and is the number of patients with disease control at each scheduled scan time point divided by the number of patients in cohort B. For patients who change treatment to IMM-101 + ipilimumab, disease control is assessed until and including the last evaluable tumour assessment (scan) prior to the change in therapy, and the disease control rate evaluated accordingly.

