5.2.4 Scheduled Scan Windows

Each scan, whether scheduled or unscheduled, will be allocated to a scheduled scan time point if it is within the scheduled scan timetable window +/- 7 days (see protocol Appendix 1). If there is more than one scan within a scheduled scan time window, the closest scan prior to the scheduled timepoint, or after it if there are no scans prior, will be considered the scheduled scan for that timepoint. For efficacy assessments, all scans will be included whether they are scheduled or unscheduled. Listings of scan data will include the allocated visit (as defined above) and a flag to indicate if this differs from the original visit recorded at site.

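### The SAP's scan-selection rules can count a Cohort B patient with progression on the Week 14 scan as disease-controlled at Week 14

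*SAP*

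**What the plan says.** Disease control is an exploratory endpoint for Cohort B only. SAP 5.13.3.4 defines it thus: "Disease control is defined as a subject with a response of CR, PR or SD as per RECIST 1.1. Confirmed responses are not required". It is a status at a time point: "Disease control is assessed at each scheduled scan assessment from Week 14 until the end of the study".

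Two rules decide which scan supplies the Week 14 status.

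- **Window rule, SAP 5.2.4.** "Each scan, whether scheduled or unscheduled, will be allocated to a scheduled scan time point" if it lies within 7 days of it. Where several scans share a window, "the closest scan prior to the scheduled timepoint, or after it if there are no scans prior, will be considered the scheduled scan". The section adds that efficacy assessments include all scans.
- **Week 9–14 rule, SAP 5.13.3.4.** "SD determination requires a minimum scan time of 9 weeks from the first administration of IMM-101", so Week 14 is the first scheduled scan that can count. Of unscheduled scans between Week 9 and Week 14 it then says "they will be used for determination of SD for disease control at Week 14", and it refers to 5.2.4 for the windows.

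Protocol 10.6 is softer: "If unscheduled scans take place earlier than Week 14 but later than Week 9, these may be used for determination of SD". SAP Section 6, which lists five changes from the protocol, does not mention this one.

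On extra scans, the treatment-phase text of Protocol 5.1 says: "Subsequent scans are every 8 weeks with unscheduled scans allowed if clinically indicated, for example to confirm progression". Protocol 5.3 and 8.5.3.10 also foresee a repeat scan about 4 weeks after PD and a confirmation scan at least 4 weeks after a response.

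**The concern.** Best overall response and PFS run over a period, so using all scans is workable for them. Disease control needs one answer per patient per time point. Neither document says that PD on the Week 14 scan overrides an earlier SD, or that a Week 9–14 scan counts only when the Week 14 scan is missing.

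The same patient could then be disease-controlled at Week 14 and have a PFS event on the Week 14 scan. Two programmers working from the same data could also report different rates. Cohort B is small enough for one patient to show.

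**Working it through.** The plan states no target or expected rate for this endpoint, so there is no figure to reproduce. The check applies the two rules to possible scan dates.

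**Inputs.** Day 0 is the first IMM-101 dose (SAP 5.2.2). Week 14 = 14 × 7 = Day 98, with window Days 91–105. The 9-week minimum is 9 × 7 = Day 63. The Week 6 window is Days 35–49. Cohort B has 8 planned patients (SAP 3) and 5 at recruitment suspension (SAP 4).

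**Window rule, one example.** SD on an unscheduled Day 92 scan, PD on the scheduled Day 99 scan:

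- distances from nominal are |92 − 98| = 6 days and |99 − 98| = 1 day
- Day 92 is the only scan before Day 98, so the rule takes it, and the patient counts as controlled
- if Day 99 is the first PD, it is a PFS event under Protocol 10.2 and SAP 5.13.2.1

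If the scheduled scan had been on Day 97, it would have been chosen. The rule therefore bites only when the scheduled scan falls after Day 98, or on Day 98 if a scan on the nominal day is not read as prior to it.

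**Window rule, all date pairs.** The window has 15 days, so there are 15 × 14 / 2 = 105 pairs of distinct days.

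| Reading of a Day 98 scan | One scan on each side (earlier chosen) | Both on the later side (earlier chosen) | Earlier chosen, total | Chosen scan is the farther one |
|---|---|---|---|---|
| Not prior | 7 × 8 = 56 | 8 × 7 / 2 = 28 | 84 | 1 + 2 + … + 7 = 28 |
| Prior | 8 × 7 = 56 | 7 × 6 / 2 = 21 | 77 | 1 + 2 + … + 6 = 21 |

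These are counts of calendar possibilities, not probabilities. They show that in 28 (or 21) of 105 pairs the rule rejects the scan nearer to the time point.

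**Direction.** Swap the results, with PD on Day 92 and SD on Day 99. The rule still takes Day 92, and the patient is now not controlled. The window rule has no fixed direction.

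**Week 9–14 rule.** Scans on Days 64–90 (90 − 64 + 1 = 27 days) lie outside both the Week 6 and Week 14 windows. Take SD on Day 70 and PD on a scan in the Week 14 window:

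- by 5.2.4, only the later scan is allocated to Week 14, so the patient is not controlled
- by 5.13.3.4, the Day 70 scan is to be used for SD at Week 14, so the patient is controlled

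No sentence ranks one above the other.

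**Size.** One patient is 1/8 = 12.5 points, or 1/5 = 20 points. Exact (Clopper–Pearson) 95% limits are the 0.025 quantile of Beta(x, n − x + 1) and the 0.975 quantile of Beta(x + 1, n − x). With assumed counts:

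| n | PD counted | Earlier SD counted |
|---|---|---|
| 8 | 3/8 = 37.5% (8.5 to 75.5) | 4/8 = 50.0% (15.7 to 84.3) |
| 5 | 2/5 = 40.0% (5.3 to 85.3) | 3/5 = 60.0% (14.7 to 94.7) |

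**The case against.** The best defence is that the Week 9–14 sentence only says which early scans can qualify as SD, and that it fills a gap. A Cohort B patient who responds at Week 6 and has a confirmation scan at Week 10 need not have the Week 14 scan (Protocol 5.3, 8.5.3.10). There is then normally nothing to conflict with, and the sentence is useful. This stands as a likely intention, but the SAP does not state it. Skipping is optional, and extra scans can arise for other reasons. On this route the wrong result is permitted by silence, not required.

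The pattern is also narrow. The window rule needs two scans within 15 days, on opposite sides of Day 98 (or the later one on it, read strictly) and with different results. After PD at Week 6, a conflict needs a return to SD near Week 10 and then PD at Week 14. Patients who switch to ipilimumab leave the assessment at the switch. The status is listed per patient and visit, and reallocated scans are flagged. All of this stands and keeps the point small.

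A reader might infer that the SAP systematically inflates disease control, because such scans will be common and early scans are mostly done in deteriorating patients. The documents support none of this. They give no frequency and no reason pattern for early scans. If early scans did follow deterioration, they would more often show PD, and the window rule would then lower the rate. Nor do the documents show that Week 14 will be the largest of the disease control rates.

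**Conclusion.** The point holds as a defect in two selection rules, not as a demonstrated bias. Under SAP 5.2.4 a patient with SD before Day 98 and PD on a scheduled scan after it, both in the window, is counted as controlled by the stated rule. Under SAP 5.13.3.4 the same result is open because no precedence is given.

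Each affected patient moves the rate by 12.5 points with 8 patients. The 20-point figure applies only if final enrolment stays at 5, since disease control is not among the interim endpoints. The mismatch with PFS assumes that the Week 14 PD is the patient's first.

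The frequency is unknown and probably low, the endpoint is exploratory and descriptive, and no primary or secondary result changes. It is a minor point, but worth settling before database lock.

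**What to change.** Two changes to the SAP:

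1. **5.2.4:** when more than one evaluable scan lies in a window, use the one closest in absolute days to the scheduled date, and the later one if tied.
2. **5.13.3.4:** use a scan after Week 9 and before the Week 14 window only if no evaluable scan lies in that window. Count a patient with RECIST 1.1 PD after the SD scan, up to the end of the window, as not controlled at Week 14, whichever scan change 1 selects.

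The tie-break and the PD override are conventions that no document dictates. What matters is that one rule is written down before the results are known. SAP Section 6 should record the departure from the protocol's permissive wording.

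The cost is two sentences and one derivation. The reported rate may be slightly less favourable in some cases. In the mirror case (early PD, nearer SD) change 1 would select the SD scan.

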Ultrasound should not be used for lesion measurement. If new lesions are identified by ultrasound in the course of the study, confirmation by CT or MRI should take place.

Endoscopy and laparoscopy should not be used for objective tumour evaluation.

Immune Related Response Criteria (irRC) is also used in this study for assessment of response and may be used for the purposes of managing patients on protocol treatment and decision making for discontinuation of study therapy due to disease progression. For the purposes of irRC, up to five lesions in a single organ may be recorded with a maximum of 10 visceral and five cutaneous index lesions (see Section 8.5.2.3). The first post-baseline radiological assessment of tumour response status will be performed at Week 12 (±7 days) for patients in cohort A and at Week 6 (±7 days) for patients in cohort B unless there is clinical indication (based on Investigator's assessment) warranting earlier imaging. Subsequent radiological assessments are at 8 weekly intervals thereafter on study. Beyond week 52, scans may be conducted every 12 weeks at the discretion of the investigator.

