If imaging shows a complete response (CR) or partial response (PR), according to the rules in 8.5.3.1, tumour imaging should be repeated at least 4 weeks later to confirm response, per RECIST 1.1 recommendations. The results of both the first (original) scan showing a CR or PR according to the rules in 8.5.3.1 as well as those of the confirmatory scan should be entered into the eCRF. The values for the original scan should not be amended in the eCRF even if the confirmatory scan does not confirm the results of the original scan. The confirmed response is used for the calculation of BOR (and hence the primary endpoint of ORR). However, BOR and hence ORR, using unconfirmed responses will also be calculated for comparability with published data. Following a confirmatory scan, the patient will then return to regular scheduled imaging every 8 weeks relative to the Week 12 scan (Cohort A) or Week 6 scan (Cohort B) and 12 weekly for patients still on study after Week 52. Patients who obtain a confirmation scan do not need to undergo scheduled imaging assessment 4 weeks later (e.g., if a patient obtains a scan at Week 16 to confirm a Week 12 response, their next scheduled scan would not be performed until Week 28, with no scan at Week 20). Once a response is confirmed, repeat scans are not required to confirm subsequent instances of the same response.

Page 59 of 98

If imaging shows PD, it is at the discretion of the investigator whether to continue or stop study treatment (i.e. both IMM-101 and nivolumab/ipilimumab) recognising that some patients with advanced melanoma can have a transient tumour flare in the first few months after start of immunotherapy with subsequent disease response. This decision will be based on clinical judgment but to continue treatment on study after disease progression is identified by a scan, the patient should have:

- Absence of clinical symptoms and signs indicating disease progression (including worsening of laboratory values)
- No decline in performance status
- Absence of disease symptoms indicative of requiring alternative treatment
- No clinically relevant adverse effects related to study treatment

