# 8.5.3.9 Missing Assessments and Not Evaluable Designation

When no imaging/measurement is done at all at a particular time point, the subject is not evaluable (NE) at that time point. If only a subset of lesion measurements are made at an assessment, the case is also considered NE at that time point, unless a convincing argument can be made that the contribution of the individual missing lesion(s) would not have changed the assigned time-point response (for example if the criteria for PD are reached by the lesions that have been assessed).

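### From Week 22 on, the Cohort B disease control rate counts a controlled patient in a protocol-permitted scan gap as not controlled

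*SAP*

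**What the plan says.** SAP 5.13.3.4 uses the Cohort B ITT set and defines control as CR, PR or SD by RECIST 1.1. "Disease control is assessed at each scheduled scan assessment from Week 14 until the end of the study". The table has two counts: "The number of subjects with controlled disease and the number without controlled disease will be summarised", with the rate and its 95% CI. For the rate, "Disease control rate is calculated as the number of subjects with disease control divided by the number of subjects in the analysis set". Protocol 10.6 has the same fixed denominator: "the number of patients with disease control at each scheduled scan time point divided by the number of patients in cohort B".

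The protocol allows two departures from the 8-weekly scan grid:

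- **After a confirmation scan.** Protocol 8.5.1 waives the scheduled scan four weeks later. Its example is a Cohort A patient with a Week 12 response confirmed at Week 16: "their next scheduled scan would not be performed until Week 28, with no scan at Week 20". Protocol 5.3 and 8.5.3.10 repeat the rule for both cohorts.
- **Late in the study.** "Beyond week 52, scans may be conducted every 12 weeks at the discretion of the investigator" (Protocol 8.5.1).

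Three further rules decide what happens at an empty time point. SAP 5.2.4 assigns a scan to a scheduled time point only if it falls within 7 days of it. Protocol 8.5.3.9 says "When no imaging/measurement is done at all at a particular time point, the subject is not evaluable (NE) at that time point". SAP 5.2.6 applies no imputation in general. The only bridging rule is for Week 14: "If unscheduled scans take place earlier than Week 14 but later than Week 9, they will be used for determination of SD".

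**The concern.** Counting an unscanned patient as a failure is a defensible conservative convention when a scan was due and missed. Here the schedule itself creates the gap. The post-confirmation gap can occur only in patients who have just shown CR or PR. The late gap can affect any patient still controlled after Week 52, including those with SD. The patients scored as failures are therefore ones with evidence of control, and the error runs in one direction.

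The per-visit rate with its CI is the whole planned disease control summary. It could fall at Week 22 and rise again at Week 30 with no change in anyone's disease, and a reader of the table alone would take this as loss of control.

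**Working it through.** The documents give no disease control figure to reproduce. The check rebuilds the scan grid, applies the permitted gaps and works out the effect on the rate.

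**Inputs**
- Cohort B scans: Week 6, then every 8 weeks, i.e. 6, 14, 22, 30, 38, 46, 54, 62, 70, 78 (Protocol 5.1 and Appendix 1). Nine time points count from Week 14.
- Window: 1 week either side (SAP 5.2.4).
- Cohort B size: 8 planned (SAP 3); 5 recruited when recruitment was suspended (SAP 4), used here as a lower sensitivity value and not as a final size.

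**Check of the skip rule.** Response at week w, confirmation at w+4, no scan at w+8, next scan at w+16. With w = 12 this gives 16, 20 and 28, which is the protocol's own Cohort A example.

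**Gap 1, Cohort B.** With w = 14: confirmation at Week 18, no scan at Week 22, next scan at Week 30. Week 18 lies outside both the Week 14 window (13–15) and the Week 22 window (21–23). Confirmation 4, 5 or 6 weeks after Week 14 matches no window. At 7, 8 or 9 weeks it falls in the Week 22 window and leaves no gap. The same pattern can empty any later time point up to Week 78.

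A Week 6 response confirmed at Week 10 would skip Week 14, but the Week 9–14 rule largely covers that case (it names only SD). Hence the problem starts at Week 22.

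**Gap 2.** The time points after Week 52 are 54, 62, 70 and 78.
- 12-weekly from Week 54: scans at 66 and 78, so 62 and 70 are empty.
- 12-weekly from Week 46: scans at 58 and 70, so 54, 62 and 78 are empty.

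Scans at Weeks 58 and 66 match no window even if moved by 7 days.

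**Effect on the rate.** With k patients controlled and g of them in a gap, the tabulated rate is (k − g)/n. Each gap patient costs 1/8 = 12.5 points or 1/5 = 20 points. Illustrative values with Clopper-Pearson 95% CIs:

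| n | Controlled | In a gap | Tabulated rate (95% CI) |
|---|---|---|---|
| 8 | 3 | 0 | 3/8 = 37.5% (8.5–75.5) |
| 8 | 3 | 1 | 2/8 = 25.0% (3.2–65.1) |
| 8 | 3 | 2 | 1/8 = 12.5% (0.3–52.7) |
| 5 | 2 | 0 | 2/5 = 40.0% (5.3–85.3) |
| 5 | 2 | 1 | 1/5 = 20.0% (0.5–71.6) |

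**How often gap 1 could arise (assumption).** The documents give no response rate for this regimen in Cohort B. Protocol 3.4 quotes 10–15% for ipilimumab after anti-PD-1 failure, which is a different regimen. Using that range, P(at least one responder) = 1 − (1 − p)^n:
- n=8: 1 − 0.90^8 = 57.0%; 1 − 0.85^8 = 72.8%.
- n=5: 1 − 0.90^5 = 41.0%; 1 − 0.85^5 = 55.6%.

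P(two or more), which also subtracts n·p·(1 − p)^(n−1), is 18.7–34.3% at n=8 and 8.1–16.5% at n=5. These count responders at any time. The chance of a gap at one particular time point is lower, because the response must appear at the preceding scan and the skip is optional.

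**The case against.** **The SAP nowhere states that an unscanned patient is without control.** That is true; it is the combined effect of several rules. SAP 5.1 defaults to percentages of non-missing observations, its listed exceptions do not include efficacy, and the table shells are not among the documents. But 5.13.3.4 sets its own denominator, and Protocol 10.6 agrees with it. A not-evaluable row in the shells would change the counts shown and leave the rate as it is.

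**SAP 5.2.4 includes all scans, scheduled or not, in efficacy assessments.** That does not place a Week 18 scan at Week 22. If it did, the Week 9–14 exception would be unnecessary.

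**The fixed denominator is a deliberate worst-case convention.** The SAP states worst-case handling explicitly for best overall response in patients with no assessment, but not for disease control. The convention also fits poorly where no scan was required.

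**The stakes are low.** This stands. The endpoint is exploratory, with no hypothesis test, stopping rule or interim use. The per-subject listing will show each gap, and Kaplan-Meier PFS is unaffected. With 5 to 8 patients, a careful reader of the listings would spot the artefact.

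**The frequency figures are soft.** This also stands. The response rate is borrowed, two patients in a gap at the same visit is less likely than the two-responder figures, and nothing in the documents shows how many Cohort B patients will remain on study after Week 52.

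**Conclusion.** The concern holds. As written, the Cohort B rate from Week 22 onward is biased downward by 12.5 points per affected patient at n=8 (20 at n=5) whenever a patient with controlled disease uses a permitted gap. This follows from the text and the scan grid and needs no assumption about response. How often it happens does depend on assumptions: the borrowed 10–15% response rate for the post-confirmation gap, and the unknown use of 12-weekly scanning for the late gap. The gaps are optional, so the bias may turn out to be zero. Given the exploratory, descriptive role of the endpoint, the derivation should be corrected before database lock, but it does not threaten the trial's main conclusions.

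**What to change.** In SAP 5.13.3.4:

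1. Where a subject has no scan in the window because of a permitted gap, count disease control only if the evaluable scans on both sides are CR, PR or SD, with no PD, death or switch to ipilimumab between them. Permitted gaps can be derived from scan dates.
2. Put subjects in a permitted gap with no later evaluable scan in a separate row, *not scanned per protocol*, without crediting control. This will apply to an empty Week 78: with scans at Weeks 58 and 70, the end-of-study scan is not required, because 12 weeks have not passed. The rate at that time point stays as it is, but the reason becomes visible.
3. Report how many subjects were classified by the rule, and show the observed-scan-only rate alongside.
4. Record the change in SAP Section 6, because Protocol 10.6 uses the same fixed denominator.

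The cost is some SAP wording, a short derivation, one table row and one Section 6 entry; no new data are needed. The downside is a limited interpolation in which a later scan classifies an earlier time point: PR at Weeks 14 and 18 followed by PD at Week 30 would still not count as control at Week 22. The documents already accept similar reasoning, since a PR–NE–PR sequence counts as a confirmed response (Protocol 8.5.3.10; SAP 5.13.1).
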